Comparison of propofol and sevoflurane as a primary anesthetic for cardiac ablation of atrial fibrillation

NCT02697448

June 28, 2023

Medical University of South Carolina Protocol

PI Name: [name]

Study Title: Comparison of propofol and sevoflurane as a primary anesthetic for cardiac ablation of atrial fibrillation

TABLE OF CONTENTS

- A. Specific Aims 1
- B. Background and Significance 1-2
- C. Preliminary Study 2
- D. Research Design and Methods 2-3
- E. Protection of Human Subjects 3-5
- F. References 6

A. SPECIFIC AIMS

The primary aim of this study is to compare two commonly used anesthetic techniques (propofol and sevoflurane) during atrial fibrillation ablation cases. Of greatest interest is to compare the time to awaken the patients after the procedure. Also of interest is the duration of the ablation procedure. The hypothesis of this investigation is that patients who receive propofol will require a longer time to removal of the endotracheal tube after the end of the procedure than patients anesthetized with sevoflurane.

B. BACKGROUND AND SIGNIFICANCE

The incidence and prevalence of atrial fibrillation continues to rise in our country. Currently, the incidence is predicted to double from 1.2 million cases in 2010 to 2.6 million cases in 2040. Atrial fibrillation prevalence is projected to increase from 5.2 million in 2010 to 12.1 million in 2030. ¹ As the rates of atrial fibrillation cases increase, treatments such as catheter-based ablation will also increase.

Ablation procedures require the administration of general anesthesia. A wide variety of general anesthesia techniques have been used since the inception of the ablation procedure, but there are few comparative studies of anesthetic techniques. The lack of evidence comparing two widely used anesthetic techniques means that choice of a primary anesthetic is based on personal preference or local custom. In a recent review of Ablation Procedures and Anesthetic implications the authors state: "The literature regarding the best choice for anesthetic technique in ablative procedures is still scarce and the decision ultimately depends on the patient's clinical condition, the anesthesiologist's judgment, and the electrophysiologist's comfort level."² For this reason a study comparing two of the commonly employed techniques is warranted.

Propofol is a sedative hypnotic agent used as an infusion as a general anesthetic at a recommended dose of between 100 and 200 mcg/kg/min. In a continuous infusion, the distribution half-life of propofol is 1 to 3 hours in a 2-compartment model and 30 to 70 minutes in a 3-compartment model. The context-sensitive half time for infusions of up to 8 hours is 40 minutes.¹

Propofol produces myocardial depressant effects and decreased systemic vascular resistance; these are both dose and concentration dependent. Propofol has also been found to alter the baroreflex mechanism, which causes a smaller increase in heart rate for a given decrease in blood pressure.

Propofol is commonly used as a general anesthetic agent for many different types of surgical procedures, including atrial fibrillation ablations. Propofol is used as a general anesthetic for cardiac ablation procedures because it has no known effects on the cardiac conduction system.

Sevoflurane is a volatile anesthetic, which is administered via inhalation. A concentration of 2% is typically used as a general anesthetic dose of sevoflurane. Sevoflurane undergoes very little metabolism by the body, rather once the vaporizer is turned off and the patient breathes off the gas, the anesthetic effects are gone. Like other inhaled anesthetics, sevoflurane is very rapid acting. This ability to quickly increase or decrease anesthetic levels as necessary aids in efficiency and also increases the margin of error for this drug.

Sevoflurane, and other volatile anesthetics, are the most commonly used general anesthetic agents in use today, both for their confirmed safety profile and also the ease of titrating the drugs. Sevoflurane is used in some centers for ablation procedures. Our institution has also used Sevoflurane for atrial fibrillation ablations in the past when there has been a shortage of propofol.

At our institution a total intravenous anesthetic (TIVA) with propofol is used during atrial fibrillation ablation cases. Sevoflurane is used at other centers, such as UCLA. Due to sevoflurane's shorter half life and the fact that it is not metabolized as much as propofol by the body, patients may have the breathing tube removed in a shorter period of time after the procedure is over and also be more awake and alert in the recovery room than if they had undergone the procedure using propofol as the primary anesthetic. Propofol has been shown to have no effect on cardiac conduction⁴ and preliminary evidence shows that sevoflurane may similarly have no effect.³ Because shorter wake-up time could reduce hospital costs and improve efficiency, it is important to compare these two techniques focusing on time for extubation.

There have been no head to head comparisons of total intravenous anesthesia (TIVA) versus sevoflurane for ablation procedures. By conducting a randomized blinded study of these two anesthetics, new and important knowledge can be generated for this increasingly commonly performed procedure.

A side effect of other volatile anesthetics, such as isoflurane and desflurane, is enhanced automaticity, accounting for secondary atrial pacemakers. ⁵ Volatile anesthetics also have varying effects on the AV node and His-Pukinje system.⁶ These agents also prolong the QT interval⁶ and, for this reason, volatile anesthetics as a group have at times been avoided for atrial fibrillation ablation. However, sevoflurane does not seem to have the effects shown for other volatile anesthetics on cardiac conduction, based on preliminary evidence.³ Sharpe, et al suggested with results from a 15 patient study that Sevoflurane had no effect on the refractoriness of the normal or accessory atrioventricular pathway and also no clinically significant effects on sinoatrial node function or intraatrial conduction.³ Though the aforementioned study's population consisted of patients with Wolff-Parkinson-White (WPW) syndrome, the concerns with how the anesthetic drugs affect the conduction system are the same with WPW as they are for atrial fibrillation cases. Some institutions, such as UCLA, now use sevoflurane as the primary anesthetic for atrial fibrillation ablation cases.

This study, a partnership between anesthesia and electrophysiology cardiologists, will be the first study to compare these two commonly used anesthetic techniques. The primary end-point of this study is the time interval from the end of the procedure to tracheal extubation. We will also measure the length of procedure, any differences in hemodynamics, patient alertness in the immediate postoperative period, as well as the rate of postoperative nausea and vomiting to see if there is a difference between the two anesthetics. At 3 month and 6 months, medical records will be examined to see if there is any difference in the recurrence of atrial fibrillation. Although our study is not powered for this, we will examine for this due to the theoretical risk of recurrence with Sevoflurane.

The significance of this study is that it will be the first study to compare two commonly used anesthetic techniques in the setting of atrial fibrillation ablation. There is currently no comparative evidence available to determine which technique is superior in this setting and as a result clinical practice is based on custom and familiarity rather than evidence of superiority.

C. PRELIMINARY STUDIES

There have not been any blinded randomized studies comparing volatile anesthetics to TIVA for atrial fibrillation ablations. By performing this study, we can demonstrate if one anesthetic is superior to another for time of extubation and note any other differences in measured variables including the patient's satisfaction in the immediate post- operative period.

D. RESEARCH DESIGN AND METHODS (including data analysis)

Patients with persistent and paroxysmal atrial fibrillation, undergoing their first ablation, will be invited to participate in the study during their pre-operative visit if the patient is scheduled for one, but otherwise during their pre-operative anesthesia work up in the holding room. Once informed consent is obtained, the participant will be randomized via computer-generated randomization into one of two groups. Group A will receive propofol 100-150mcg/kg/min; Group B will receive sevoflurane 2% end tidal concentration as their primary, general anesthetic for the procedure. Doses of each drug will be titrated to effect in order to obtain general anesthesia. The electrophysiologist performing the procedure will be blinded as to which drug the patient is receiving. Data will be collected from the patient's electronic medical record postoperatively. Our primary endpoint is time from procedure end until the time that the endotracheal tube is removed (wake-up time.) Data will be analyzed using an independent 2-sample t-test.

We will also measure and compare duration of the procedure, postoperative nausea and vomiting, hemodynamic differences during the case, and patient alertness postoperatively using a short questionnaire to be filled out on the morning of POD 1 by a trained study team member. Following their first clinic visit with their cardiologist and for a total of 6 months postoperatively, we will view their medical record to look for recurrence of atrial fibrillation.

Analysis plan, sample size and power:

The primary outcomes are procedure duration and time to extubation. Both outcomes will be analyzed using an independent 2-sample t-test.

Propofol infusion is the most common primary anesthetic at MUSC for patients undergoing cardiac ablation for atrial fibrillation. The primary outcome is time from procedure end to extubation between the two groups that will be compared using a two-sample t-test approach. Sixty-three patients per group (126 total) provides 80% detection an effect size of 0.5 between the two groups using a two-sided t-test at significance level $\alpha = 0.05$. The statistical assumptions will be checked graphically and the non-parametric Wilcoxon rank sum test will be used if assumptions are violated.

E. PROTECTION OF HUMAN SUBJECTS

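### Does starting the primary clock at procedure end, with no planned record of when the anesthetic was stopped, undermine the primary comparison?

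*Combined protocol and SAP*

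**What the plan says.** Section D sets the endpoint: "Our primary endpoint is time from procedure end until the time that the endotracheal tube is removed (wake-up time". The end of Section B gives the same definition, and the sample-size paragraph of Section D uses it again. The hypothesis in Section A runs on the same clock: patients given propofol "will require a longer time to removal of the endotracheal tube after the end of the procedure" than patients given sevoflurane.

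The pharmacological background is in Section B. For propofol: "The context-sensitive half time for infusions of up to 8 hours is 40 minutes". For sevoflurane: "once the vaporizer is turned off and the patient breathes off the gas, the anesthetic effects are gone". The expected direction is then explained by sevoflurane's "shorter half life and the fact that it is not metabolized as much as propofol by the body", with the prediction that "patients may have the breathing tube removed in a shorter period of time after the procedure is over". The same paragraph gives the practical reason for the comparison: a shorter wake-up could lower hospital cost and improve efficiency.

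On blinding, Section D says: "The electrophysiologist performing the procedure will be blinded as to which drug the patient is receiving". Data are to come from the "electronic medical record postoperatively". The items listed in Section E.1.b are procedure length, procedure end to extubation, side effects and alertness. Anesthetic stop time is not listed there or in Section D.

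**The concern.** Half life, metabolism and context-sensitive half time describe what happens after a drug is stopped. The primary clock starts at a different event, the end of the procedure. If propofol were habitually turned off earlier or later than sevoflurane, the interval would shift even if patients recovered equally fast after stopping. The documents set no stop time, and nobody but the electrophysiologist is stated to be blinded, so habits could differ by arm.

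Propofol is the usual agent at this center, and sevoflurane was used there during a propofol shortage, so unequal habits are conceivable. What would be at stake is interpretation. A positive result might be read as faster drug offset when it partly reflects local timing, and a null result might hide two components that cancel.

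**Working it through.** **1. The plan's own figure.** Inputs from Section D: standardized effect 0.5, two-sided alpha 0.05, power 80%. By normal approximation, n per group = 2 × (1.96 + 0.842)² / 0.5² = 62.8, so 63, with power 0.801. The noncentral t gives 63.8, so 64, with power 0.795 at 63. The stated 63 reproduces. The effect size is in SD units of the whole interval, so no stop time enters.

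**2. The decomposition.** As signed times for each patient:

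(extubation − procedure end) = (stop − procedure end) + (extubation − stop)

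The arm differences in means add in the same way. The listed data give the sum and not the two parts. To this extent the concern is factually right.

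**3. What a stop-time difference would do.** The documents give no SD in minutes and no stop times, so these are illustrations with 63 per group:

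| Stop-time difference (SD of the interval) | Probability of a significant result if recovery after stopping is equal | Power if recovery differs by 0.5 SD and the stop-time shift is opposite |
|---|---|---|
| 0 | 0.05 | 0.795 |
| 0.1 | 0.09 | 0.61 |
| 0.25 | 0.29 | 0.29 |
| 0.5 | 0.80 | 0.05 |

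For an assumed SD of 10 to 20 minutes, 0.5 SD is 5 to 10 minutes.

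**4. How to read that table.** The null hypothesis of the planned test is that the mean interval from procedure end to extubation is the same in both arms. In the second column, rows 2 to 4, that null is false: the intervals do differ, by 0.1, 0.25 or 0.5 SD. Rejecting it is a correct decision, not a false positive. In the third column the true differences in the interval are 0.5 − 0.1 = 0.4, 0.5 − 0.25 = 0.25 and 0.5 − 0.5 = 0 SD, and the test responds to them as it should. When the interval does not differ, rejection stays at 0.05. The table would show error only if the target were recovery after stopping.

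**5. What the target is.** Setting the sections side by side:

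- Section A: compare two techniques; the hypothesis is stated from the end of the procedure.
- Section B: the interval matters because of cost and efficiency, for which the end of the procedure is a suitable start.
- Section C: show whether one anesthetic is superior for time of extubation.
- Section D: the endpoint, test and sample size all use that interval.

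None of these plans an estimate of drug offset. Half life and metabolism explain why a direction is expected.

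**6. Weight of the missing item.** The list in Section E.1.b is not a full inventory. It omits recurrence of atrial fibrillation, which Sections B and D plan to take from the medical record. Absence from it is weak evidence that an item will not be collected.

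**The case for a change.** The strongest case is that Section D labels the interval wake-up time, Section B explains the expected difference by pharmacology, and Section E.4 says the results will inform anesthesiologists choosing between the drugs. A reader at another center would want to know whether a difference came from the drug or from local stopping habits. One timestamp and two descriptive estimates might show this cheaply. At 63 per group, if every patient had a charted stop time, each estimate would have a 95% confidence half-width of 1.979 × √(2/63) = 0.353 of its component's SD, which is informative.

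What stands is that stop time is not listed and the split would help interpretation. It would not achieve the separation asked for. Stopping happens after randomization, the time from stop to extubation depends on an extubation decision not stated to be masked and on any tapering, and the documents do not say whether stop time is charted.

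The documents also give no evidence that stopping differs by arm. Section E.1.c describes the drugs as being given while the procedure lasts. This sets no stopping rule, but it can be read as stopping near procedure end, which would leave little to separate. Comparing a shift of 5, 10 or 20 minutes with propofol's 40 minutes (12.5%, 25% or 50%) does not size the problem either: the 40 minutes is a half time for drug concentration, not an extubation interval or its SD.

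**Conclusion.** The concern does not hold. The endpoint, hypothesis, practical rationale and promised conclusion all refer to the interval from procedure end to extubation, compared between whole techniques. A difference in stopping time is part of that effect and not a bias in it. Followed as written on this point, the plan answers the question it asks. The 63 per group reproduces, and no stated figure, error rate or sample size changes.

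This rests on reading the trial as a comparison of techniques, which Section A states. If a report were to claim that sevoflurane wears off faster in the pharmacological sense, that claim would go beyond the planned data. No section plans to make it. Recording stop time remains an optional aid to interpretation.

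### One sentence of the analysis plan makes procedure duration a second primary outcome; every other statement of the primary outcome names extubation time alone, and no rule says which result decides the trial.

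*Combined protocol and SAP*

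**What the plan says.** All of this is current text in the combined protocol and SAP.

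**Two primary outcomes.** Section D, first paragraph under the analysis-plan heading: "The primary outcomes are procedure duration and time to extubation. Both outcomes will be analyzed using an independent 2-sample t-test".

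**One primary outcome.**

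- Section D, the next paragraph under the same heading: "The primary outcome is time from procedure end to extubation between the two groups that will be compared using a two-sample t-test approach". The sample size follows directly: 63 per group, effect size 0.5, two-sided alpha 0.05.
- Section D, design paragraph: wake-up time, defined as procedure end to tube removal, is named as the primary endpoint. The paragraph after it treats duration as an additional measure: "We will also measure and compare duration of the procedure".
- Section B, Background and Significance: "The primary end-point of this study is the time interval from the end of the procedure to tracheal extubation". Length of procedure is then listed with hemodynamics, alertness, and nausea and vomiting.
- Section C, Preliminary Studies, states the goal for extubation: "we can demonstrate if one anesthetic is superior to another for time of extubation".
- Section A, Specific Aims: "The hypothesis of this investigation is that patients who receive propofol will require a longer time to removal of the endotracheal tube". On duration it says only: "Also of interest is the duration of the ablation procedure".

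The one alpha in the documents is the 0.05 in the sample-size sentence. No alpha is attached to duration, and there is no alpha split, testing order or success rule for two outcomes.

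**The concern.** The plural and the singular statement stand in consecutive paragraphs and cannot both be right. The plural one is not a one-word slip: it names two outcomes, and the sentence after it assigns a test to each.

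The two readings support different primary claims. Suppose duration differs significantly between the arms and extubation time does not. The opening of the analysis plan would allow that to be reported as a primary success; the other statements would call the trial negative on its primary outcome. With no tie-break, the choice could be made after the results are seen. If either outcome may carry the claim at 0.05, the primary false-positive rate is above 5%.

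**Working it through.** **Inputs from the documents (section D).** 63 per group, standardized effect size d = 0.5, two-sided alpha 0.05, nominal power 80%, two-sample t-test.

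**Assumptions, because the documents give no figure.** Correlation between the two outcomes: a range from 0 to 0.9. Where power for duration is needed: d = 0.5 for duration as well.

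**Step 1. Reproduce the planned sample size.**

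Normal approximation: n = 2(1.960 + 0.842)² / 0.5² = 62.8, so 63 per group. This matches the plan.

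Power at 63 per group: the noncentrality is 0.5 × √(63/2) = 2.806. The normal approximation gives Φ(2.806 − 1.960) = 80.1%; the noncentral t gives 79.5%. The calculation covers one outcome at one alpha of 0.05.

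**Step 2. False-positive rate if either outcome suffices, each at 0.05.**

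With both null hypotheses true and independent outcomes:

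P(either significant) = 1 − 0.95² = 0.0975

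For correlated outcomes the same probability comes from the bivariate normal distribution. The part due to duration alone (duration significant, extubation not) is P(either) − 0.05.

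| Correlation | P(either significant) | P(duration only) |
|---|---|---|
| 0 | 0.0975 | 0.0475 |
| 0.5 | 0.0907 | 0.0407 |
| 0.7 | 0.0835 | 0.0335 |
| 0.8 | 0.0781 | 0.0281 |
| 0.9 | 0.0704 | 0.0204 |

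A simulation with actual t-tests (63 per group, 200,000 runs) gave 0.099, 0.090, 0.083 and 0.071 for either outcome at correlations 0, 0.5, 0.7 and 0.9. The duration-only part was 0.048, 0.041, 0.033 and 0.021. Without the bivariate normal assumption, the upper bound is 0.05 + 0.05 = 10%.

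**Step 3. The other readings.**

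- *Extubation alone governs:* the rate is 5%, and the planned sample size applies as it stands.
- *Both must be significant at 0.05:* the rate cannot exceed 5%, but power falls. With independent outcomes, joint power at 63 per group is 0.801² = 64%; it is 69% at correlation 0.5 and 73% at 0.8. Reaching 80% takes about 83, 79 or 74 per group.
- *Either suffices, with alpha split to 0.025 each:* n = 2(2.241 + 0.842)² / 0.5² = 76.04, so 77 per group (154 in total; 154/0.94 = 163.8, so 164 with the plan's 6% attrition). At 63 per group, power per outcome is 71% by the normal approximation and 70% by the noncentral t.

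The stated 63 per group delivers its stated power only under the single-primary reading.

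**The case against.** The best defence is that a careful reader can already tell what is meant. Three explicit statements name extubation alone, Specific Aims ranks wake-up time first and states its only hypothesis on tube removal, and the one powered test at the one stated alpha belongs to extubation. The inflation also belongs to a reading the plan never adopts: no section says that either outcome suffices, or that duration is tested at 0.05. On this view the sentence is a drafting slip.

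Much of this stands. The intent is fairly clear, and the 7.0% to 9.75% figures are conditional; they are not an error rate the plan commits to. It does not remove the defect. The outlying sentence opens the section that defines the confirmatory analysis, so it is the one that would be cited in support of a primary claim on duration.

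A second objection is that co-primary intent cannot be excluded. Specific Aims mentions duration in the same paragraph as the primary aim, section E.5 makes procedure prolongation a monitoring matter, and no section calls duration secondary. That is fair, and it means that making duration secondary is an inference from the weight of the text. But being of interest or monitored for safety does not make an outcome primary, and a true co-primary design would need a success rule and a power calculation that the plan lacks.

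**Conclusion.** The concern holds and should be fixed before results are known. The plan contradicts itself on which outcome decides the trial, and nothing in the documents resolves the conflict.

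The size depends on the reading. If either outcome counts and duration is also tested at two-sided 0.05, the primary false-positive rate runs from 7.0% (correlation 0.9) to 9.75% (independence), of which 2.0 to 4.75 percentage points come from duration alone. This assumes bivariate normal test statistics. There is no inflation if extubation alone governs or if both outcomes are required. The sample size is not at fault: it is right for a single primary outcome.

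**What to change.** Replace the two opening sentences under the analysis-plan heading with wording such as:

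> The single primary outcome is time from procedure end to extubation, tested at two-sided alpha 0.05. Procedure duration is a secondary outcome, compared with an independent two-sample t-test (Wilcoxon rank sum if assumptions are violated) and reported as a between-group difference with a 95% confidence interval.

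This agrees with the hypothesis, the powered test and the other statements of the primary outcome. The confidence interval is good reporting practice and is not needed to remove the contradiction.

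The cost is two sentences. Sample size, data collection, the powered test and the safety review of procedure duration in section E.5 stay as they are. Duration loses the primary label it carries in this one place.

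If the sponsor does intend both outcomes as primary, the plan must instead state whether one or both must succeed, set alpha to match and redo the sample size. That route is not free, as step 3 of the working shows.

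### Does an unquantified graphical check, deciding between the t-test and the Wilcoxon test, undermine the primary analysis?

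*Combined protocol and SAP*

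**What the plan says.** The opening text of section D (Research Design and Methods) says of the primary endpoint: "Data will be analyzed using an independent 2-sample t-test". Under the heading on analysis plan, sample size and power, procedure duration and time to extubation are both called primary, and "Both outcomes will be analyzed using an independent 2-sample t-test". The next paragraph returns to extubation time: "The primary outcome is time from procedure end to extubation between the two groups that will be compared using a two-sample t-test approach". The sample-size sentence, also based on a two-sided t-test at 0.05, says that 63 per group "provides 80% detection an effect size of 0.5 between the two groups". So the t-test is named four times.

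The paragraph closes with the fallback: "The statistical assumptions will be checked graphically and the non-parametric Wilcoxon rank sum test will be used if assumptions are violated". No other section names a threshold, a type of plot, a data set, an assessor or a time for this check. On blinding, section D says: "The electrophysiologist performing the procedure will be blinded as to which drug the patient is receiving". It mentions no blinded analyst, database lock or unblinding step.

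**The concern.** Whether a plot looks acceptable is a matter of judgement. Two careful people can disagree over moderately skewed times, and times to extubation may well be skewed. If the person reading the plot has already seen both p-values, the check could become a way of choosing the better one. A reader of the final report could not tell from the plan which came first.

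The two tests also address different quantities: the t-test a difference in means, the Wilcoxon test the ordering of the two distributions. Section B justifies the endpoint with the words "Because shorter wake-up time could reduce hospital costs and improve efficiency", and for cost the mean difference in minutes is the natural quantity. The plan specifies no effect estimate or confidence interval for either test. Because the fallback sentence sits in the paragraph on extubation time, one may also ask whether it covers procedure duration.

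At stake would be control of the 5% error rate and a stable meaning for the primary result.

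**Working it through.** **Inputs from section D.** 63 per group, standardised effect 0.5, two-sided 0.05, 80% power. No SD and no distribution are given, so every distribution below is an assumption.

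**The plan's own figure.** n per group = 2(1.960 + 0.842)²/0.5² = 62.8, which rounds up to 63. Exact noncentral-t power at 63 is 79.5%. The stated sample size reproduces, and the choice of test does not disturb it.

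**A stand-in for the visual check.** A plot reader cannot be simulated directly. As a proxy, a strict reader switches to Wilcoxon when the skewness of the data pooled over arms exceeds 1, and a lenient reader when it exceeds 2. Each row rests on 40,000 simulated trials with 63 per arm. Under the alternative the effect is 0.5 SD, on the log scale for lognormal data.

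| Assumed data | Type I error, strict / lenient | Power, strict / lenient | Readers choose different tests | Readers reach different verdicts |
|---|---|---|---|---|
| Normal | 5.05% / 5.05% | 79.4% / 79.4% | 0% | 0% |
| Lognormal, log-SD 0.4 | 5.11% / 5.09% | 77.2% / 76.4% | 61% | 5.7% |
| Lognormal, log-SD 0.5 | 4.83% / 4.86% | 77.5% / 75.4% | 71% | 7.6% |
| Lognormal, log-SD 0.6 | 4.89% / 4.96% | 78.2% / 75.7% | 61% | 7.0% |
| Lognormal, log-SD 0.8 | 4.91% / 4.96% | 77.7% / 75.4% | 27% | 4.0% |
| Lognormal, log-SD 1.0 | 5.04% / 5.01% | 77.5% / 76.6% | 8% | 1.4% |

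The largest power gap is 78.2 − 75.7 = 2.5 points. The fifth column is the one that looks alarming, but it is only the probability that sample skewness falls between two cut-offs chosen for this exercise; it measures nothing about how people read plots. The last column is the one that bears on the trial's result.

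**Worst case.** If the analyst always reported the smaller p-value, type I error would be 6.05% for normal data and 7.47% at log-SD 1.0. That is an upper bound for deliberate selection, not a property of the written rule.

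**Would another rule do better?**

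- *Fix the t-test.* With lognormal data and a 0.5 SD log-scale effect, its power is 74.4%, 68.4% and 60.4% at log-SD 0.5, 0.75 and 1.0. Wilcoxon has 77.6%, 77.6% and 77.7%. The fallback protects against this loss.
- *Fix Wilcoxon.* Under normality its power is 77.3%, about 2 points below the t-test. For 80% it needs about 63.8 ÷ (3/π) = 66.8, that is 67 per arm, and it gives up the mean as the tested quantity.
- *Fix a t-test on log time.* Power is 78.5% for normal data (mean 10, SD 2 assumed) and 79-80% for lognormal data. With lognormal data in which 2% of patients have tenfold times, it is 64.8%, against 72.7% for Wilcoxon.
- *Write a blinded skewness trigger of 1.* The cut-off is arbitrary and ignores unequal spread. With equal means and log-SD 0.4 against 0.8, this rule selects Wilcoxon in about 97% of trials and rejects in about 53%. The tested quantity would still depend on the data.

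**The case for a change.** The strongest counter-argument is unequal spread. The type I figures above hold when the two arms share one distribution. If means are equal but log-SD is 0.4 in one arm and 0.8 in the other, the t-test rejects in 6% of trials and Wilcoxon in 54%. If medians are equal instead, the figures are 37% and 6%. The choice of test can then decide the headline result, and the plan does not document how it is made. Naming one test in advance would cost a sentence and remove that dependence.

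Part of this stands. The tests do answer different questions, and the silence on timing and assessor is real. But with spread that unequal, the disagreement reflects a real difference between the distributions, which either test reports in its own terms; it is not a false positive produced by the check. Naming one test settles which question is asked, at the costs listed above, and statisticians reasonably differ on that choice. The plan has already taken a conventional position: means by default, ranks if the t-test looks unsafe.

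The two side issues are smaller. The fallback sentence speaks of the statistical assumptions without limiting them to one outcome, so applying it to both t-tests is the natural reading. An analyst would ordinarily report a mean difference with its interval beside a t-test, and can do so beside a rank test as well. Whether the trial has one primary outcome or two is a separate question.

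**Conclusion.** The plan leaves out a detail; it does not contain an error. Followed as written, the rule keeps type I error at 4.8-5.1% across the assumed shapes. Two differently minded readers would differ by at most 2.5 points of power and would reach opposite conclusions in 0% to 7.6% of trials. The inflation to about 6-7.5% requires choosing by p-value, of which the documents give no sign.

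This rests on three assumptions: normal or lognormal times, a skewness proxy for the visual check, and arms with the same distribution under the null. If spread differs markedly between arms, the error-rate reassurance does not extend to a statement about means, but the numeric trigger does not cure that, and fixing one test trades one weakness for another. An analyst can fill the gap by reading the plots without regard to the p-values and stating in the report which test was chosen and why. No change to the plan follows.
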